4.2 Recruitment Methods

Patients will be recruited from the population being seen by Investigators at the clinical sites participating in the study. In addition, notifications about the opportunity for patients to participate in a clinical trial will be sent to referring physicians. A description of the clinical trial will also be posted at ClinicalTrials.gov, and advertisements and/or other notices may be produced to advise potential study patients on how they may obtain information about study

participation. All such materials will be reviewed and approved by the Institutional Review Board (IRB) prior to their publication or dissemination.

4.3 Inclusion Criteria

It is recommended that patients should have a WOMAC A pain sub score of < 1.5 as measured by the 5-point Likert Pain Subscale in the contralateral knee, which is assessed at screening. Patients should fulfill the following inclusion criteria:

1. Able to provide written informed consent to participate in the study
2. Willing and able to comply with all study requirements and instructions of the site study staff
3. Male or female, 40 years to 85 years old (inclusive)
4. Must be ambulatory
5. Index knee must be symptomatic for greater than six months with a clinical diagnosis of OAK and supported by radiological evidence (Kellgren-Lawrence Grade 4) that is not older than six months prior to the date of screening
6. Moderate to moderately-severe OA pain in the index knee (rating of at least 1.5 on the WOMAC Index 3.1 as measured by the 5-point Likert Pain Subscale,) assessed at screening
7. Ability to temporarily discontinue NSAID for 48 hours prior to scheduled clinical efficacy evaluations
8. No analgesia (including acetaminophen [paracetamol]) taken 12 hours prior to an efficacy measure
9. No known clinically significant liver abnormality (e.g. cirrhosis, transplant, etc.)

4.4 Exclusion Criteria

Patients fulfilling one or more of the following criteria may not be enrolled in the study:

1. As a result of medical review and screening investigation, the Principal Investigator considers the patient unfit for the study
2. A history of allergic reactions to human albumin (reaction to non-human albumin such as egg albumin is not an exclusion criterion)
3. A history of allergic reactions to excipients in 5% human albumin (N-acetyltryptophan, sodium caprylate)
4. Presence of tense effusions
5. Inflammatory or crystal arthropathies, acute fractures, history of aseptic necrosis or joint replacement in the affected knee, as assessed locally by the Principal Investigator
6. Isolated patella femoral syndrome, also known as chondromalacia
7. Any other disease or condition interfering with the free use and evaluation of the index knee for the duration of the trial (e.g. cancer, congenital defects, spine OA)
8. Major injury to the index knee within the 12 months prior to screening
9. Severe hip OA ipsilateral to the index knee
10. Any pain that could interfere with the assessment of index knee pain (e.g. pain in any other part of the lower extremities, pain radiating to the knee)
11. Any pharmacological or non-pharmacological treatment targeting OA started or changed during the four weeks prior to randomization or likely to be changed during the duration of the study

12. Use of the following medications:

- a. No IA injected pain medications in the study knee during the study
- b. No analgesics containing opioids. NSAIDs may be continued at levels preceding the study, however may not be used 48 hours prior to efficacy evaluations, and acetaminophen is available as a rescue medication during the study from the provided supply
- c. No topical treatment on osteoarthritis index knee during the study
- d. No significant anticoagulant therapy (e.g. Heparin or Lovenox) during the study (treatment such as Aspirin and Plavix are allowed)
- e. No systemic treatments that may interfere with safety or efficacy assessments during the study
- f. No immunosuppressants
- g. No use of corticosteroids > 10 mg prednisolone equivalent per day
- h. If corticosteroid use is \leq 10 mg prednisolone equivalent per day, and if clinically indicated, subjects should be allowed to decrease their corticosteroid use. Additionally, some subjects may need to increase their steroid dose to treat worsened symptoms in the treated knee, and subjects who increase their corticosteroid dose above their starting dose of corticosteroid during the study will be treated as “treatment failures” for efficacy analysis

13. Any human albumin treatment in the three months before randomization or throughout the duration of the study.

4.5 Inclusion of Patients Incapable of Giving Informed Consent

No patient incapable of giving informed consent may be enrolled in the study.

5 STUDY PLAN AND PROCEDURES

Patients will be screened for inclusion into the clinical study, which will include the ability to record pain on a daily basis for seven days prior to randomization. Patients will be randomized into a study arm and receive an IA injection of Ampion or saline. Telephone contact will be made with the patient 24 hours after the IA injection. The patient will be followed for 24 weeks and the clinical effects of treatment on OAK pain will be evaluated during clinic visits at 6, 12, and 24 weeks, and during telephone contacts at 2, 4, 8 and 10 weeks, using the WOMAC osteoarthritis Index 3.1 (pain sub score, stiffness sub score and function sub score) and an overall global severity assessment (PGA).

Safety will be assessed by recording adverse events (through 24 hours post-dose and at all follow-up in-clinic visits and telephone contacts), vital signs (Baseline, and Weeks 6 and 12), recording prior and concomitant medications including start/stop dates, indication, dose and frequency (through 24 hours post-dose and at all follow-up in-clinic visits and telephone contacts) and physical examination (Baseline and Weeks 6, 12, and 24). The assessments and procedures performed at each patient visit or contact are described in Section 5 and in [Table 5.1](#).

5.1 Description of Study Visits

5.1.1 Visit -1 (Day -28 through Day 0, in-clinic): Screening

The following procedures will be performed:

- Obtain written informed consent before the start of any study specific procedure.
- Review medical history including all previous treatments for OA
- Record prior and concomitant medications including start/stop dates, indication, dose and frequency
- Record demographic data including year of birth, age, gender and race
- Measure and record height and weight
- Perform and record physical examination
- Record KL Grade from radiological assessment that is not older than 6 months prior to screening. Patient may have an x-ray at screening in order to satisfy this requirement
- Record pain in the index knee with the WOMAC Index 3.1 using both the 5-point Likert scale and the 100mm VAS scale
- Record pain in the contralateral knee with the WOMAC Index 3.1 pain subsection using both the 5-point Likert scale and the 100mm VAS scale
- Record vital signs. (Measure body temperature, systolic blood pressure [SBP], diastolic blood pressure [DBP] and pulse rate)
- Evaluate all inclusion and exclusion criteria to ensure that patients meet all inclusion criteria and none of the exclusion criteria
- Review collection instructions of daily diary pain scores with subject

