8.1 Dosing and administration of study medication

Appropriately trained site personnel should administer the study treatment.

If both knees are osteoarthritic, then the Investigator at Screening should select the knee that best satisfies the requirements for the study (see inclusion criteria) as the study knee. The study knee should be treated in accordance with the randomization schedule.

It is recommended that the study treatment be administered into the knee joint space under sterile prep conditions (i.e. the knee should be cleaned with an antiseptic). The treatment area may be anesthetized with local anesthesia including a topical anesthesia, injection of lidocaine, or nothing, as determined by the Principal Investigator. The recommended needle of choice for this procedure is a 25-gauge needle that is 1.5 inches long. The needle may be passed obliquely towards the trochlear groove. If an effusion is present, aspiration should not be performed, and the effusion should be noted in the study source notes/eCRF. Injection should proceed easily. Failure to easily inject should be documented. The same sized needle should be used for both Ampion and saline administration and recorded in the study source notes/eCRF. The date of administration should be recorded in the study source notes/eCRF.

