10.3.4 Statistical Analysis of Co-Primary Effectiveness Endpoints

A mixed-effects model with repeated measures (MMRM) will be used to test the main effect of change in WOMAC A weekly pain score (determined as the average of Daily Pain measurements taken at Baseline and Week 12) from Baseline of Ampion vs. saline at 12 weeks. The model will include change from Baseline measures at 2, 4, 6, 8, 10, and 12 weeks. Treatment assignment, week, and Baseline WOMAC A measure will be included as fixed effects. Patient ID will be included to capture repeated measures using a compound symmetric covariance matrix for residuals. The primary hypothesis test for pain is the change in pain at 12-weeks at the one-sided $\alpha = 0.025$ level.

The same model will be used to test the effect of WOMAC C function change from Baseline of Ampion vs. saline at 12 weeks. WOMAC C will be tested at one sided $\alpha = 0.025$. Because both endpoints have to achieve statistical significance, this pairing ensures the one-sided Type I error control at the 0.025 level.

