### **3.4 Covariates**

Analyses of change will include treatment assignment, Week, and the Baseline measure of the variable being analyzed as a covariate in the model.

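### Contralateral-knee pain is scored at screening but used nowhere in the SAP, so a small gain in precision is missed

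*Protocol*

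**What the plan says.** Protocol 5.1.1 lists as a screening procedure: "Record pain in the contralateral knee with the WOMAC Index 3.1 pain subsection using both the 5-point Likert scale and the 100mm VAS scale". The introduction to Protocol 4.3, ahead of the numbered inclusion criteria, states: "It is recommended that patients should have a WOMAC A pain sub score of < 1.5" on the Likert scale "in the contralateral knee, which is assessed at screening". These are the protocol's only two references to the contralateral knee.

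Two other provisions bear on who is enrolled. Exclusion 10 in Protocol 4.4 is binding but has no numeric limit: "Any pain that could interfere with the assessment of index knee pain (e.g. pain in any other part of the lower extremities". Protocol 8.1 expects bilateral disease: "If both knees are osteoarthritic, then the Investigator at Screening should select the knee that best satisfies the requirements".

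On the analysis side, SAP 3.4 gives the general rule: "Analyses of change will include treatment assignment, Week, and the Baseline measure of the variable being analyzed as a covariate in the model". Protocol 10.3.4 says the same for pain, "Treatment assignment, week, and Baseline WOMAC A measure will be included as fixed effects", and applies that model to function. SAP 8.6.1 adds a treatment-by-week term for pain, and adds site if its main effect has a p-value of 0.15 or less. The subset factors in SAP 3.5 are age, sex, race and ethnicity. The imputation in SAP 6.1.2 draws on the patient's own outcome values. SAP 8.3 lists baseline WOMAC and PGA but does not mention the other knee.

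**The concern.** The sponsor evidently thinks other-knee pain matters, because it recommends a ceiling and asks for the score on two scales. The ceiling does not bind, so some enrolled patients may have a painful second knee. Walking, stairs and daily function use both legs. The PGA question in Protocol 6.1.2 asks about arthritis as a whole rather than the study knee. The score could therefore explain part of the variation in WOMAC C (which sets the sample size), WOMAC A and PGA (the first secondary endpoint in the testing sequence).

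A baseline that explains outcome variation and is already collected can reduce the standard error for one degree of freedom. What is at stake is precision, and the chance to prespecify. Protocol 10.3.10 has the final SAP issued before the interim unblinding, and SAP 8.6.6 classes any analysis outside the plan as post hoc.

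**Working it through.** **Step 1: where the score could appear.** It is absent from the covariates (SAP 3.4, 8.6.1), subsets (3.5, 8.6.3), sensitivity analyses (3.6, 8.6.4), imputation (6.1.2, 7.2, 8.6.1), baseline summary (8.3) and named tables (10.1). The SAP does not mention the contralateral knee at all.

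**Step 2: reproduce the plan's own figures.** Inputs from Protocol 4.1 and 10.3.4: pain difference 0.83 − 0.62 = 0.21, SD 0.85, one-sided alpha 0.025, power 90%, allocation 1:1.

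- n per arm = 2 × (0.85/0.21)² × (1.960 + 1.282)², which rounds up to 345, so 690 in total. This matches the plan.
- Pain power = Φ(0.21/0.85 × √(n/2) − 1.960), with n per arm. It is 97.2% at 984 patients and 97.8% at 1,034, against the stated 97%.

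These figures use the raw SD and claim no gain from any covariate, so omitting one more covariate leaves them unchanged.

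**Step 3: function.** The documents give 984 patients for 90% power but no effect or SD. The implied standardised effect is (1.960 + 1.282) × √(2/492) = 0.2067. The 90.0% starting point below therefore holds by construction and is not an independent check of 984.

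**Step 4: effect of the covariate.** Let r be the partial correlation between the contralateral score and the Week 12 change, given the endpoint's own baseline. It is not in the documents; 0.1 to 0.3 is assumed. The Week 12 contrast is treated as a two-arm comparison of means.

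- Standard error factor = √(1 − r²)
- Function power = Φ(0.2067 × √(984 / (4(1 − r²))) − 1.960)
- Equivalent extra evaluable patients = 984 × (1/(1 − r²) − 1)
- Function N for 90% power = 984 × (1 − r²), rounded up within each arm

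| Assumed r | Fall in standard error | Function power at 984 | Equivalent extra patients | Function N for 90% | Pain power at 984 |
|---|---|---|---|---|---|
| 0 | – | 90.0% | – | 984 | 97.23% |
| 0.1 | 0.5% | 90.3% | 10 | 976 | 97.35% |
| 0.2 | 2.0% | 91.1% | 41 | 946 | 97.70% |
| 0.3 | 4.6% | 92.5% | 97 | 896 | 98.22% |

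**The case against.** The strongest case against is that nothing here is an error. Allocation is randomised 1:1, so leaving out a covariate does not bias the comparison, and many other baselines could also be proposed. Protocol 6.1 says the efficacy questions refer to the study knee, so WOMAC scores should be less exposed to the other knee than the concern suggests. Any carry-over already present at baseline is partly absorbed by the endpoint's own baseline. The recommendation and exclusion 10 both discourage enrolment of patients with a painful second knee, which narrows the range of the score and tends to lower r. The score is also a single reading taken up to 28 days before dosing. All of this stands, and it points to the low end of the table. It does not remove the gain, which costs almost nothing to take.

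A reader might infer several stronger things that the documents do not support:

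- **That contralateral pain is an established prognostic factor here.** The documents give no figure for this. It is an inference from the recommendation, the exclusion and the nature of the endpoints.
- **That the co-primary tests or sample size are compromised.** Step 2 shows that the pain figures reproduce without any covariate gain. Step 3 gives no reason to call 984 wrong.
- **That per-protocol membership is undefined.** The per-protocol set requires patients to meet the entry criteria. The 1.5 limit is a recommendation outside the numbered list, and exclusion 10 is the binding rule. A numeric guide beside a judgement-based exclusion is not a contradiction, although the link between them is unstated.
- **That every model adjusts for its own baseline and nothing else.** SAP 3.4 says so in general. But SAP 8.6.2 names Baseline PGA for the VAS model, and the WOMAC C paragraph in SAP 8.6.1 lists only Week. Those are separate matters.

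**Conclusion.** The point holds as a minor improvement. A plausibly prognostic baseline is collected and then left unused. Adding it would raise function power by about 0.3 to 1.1 percentage points at assumed partial correlations of 0.1 to 0.2, and by 2.5 points at 0.3. For pain, where power is already about 97%, the gain is at most about 1 point over the same range. The lower values are more likely because enrolment restricts the range of the score. The size rests on three assumptions: the value of r, the function effect back-solved from 984, and the two-arm approximation to the repeated-measures model.

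**What to change.** Before the interim unblinding, amend SAP 3.4 and 8.6.1 so that the screening contralateral WOMAC A Likert score enters both co-primary models as one fixed-effect covariate, alongside the treatment, week and endpoint-baseline terms. Add it to the PGA model in 8.6.2 and to the imputation model in 6.1.2 and 8.6.1. Use the same function model for the interim conditional power in SAP 7 and for the final analysis.

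If the sponsor prefers to leave the primary models as they are, the minimum is to prespecify the covariate-adjusted version as a sensitivity analysis and to summarise the score by arm under SAP 8.3. A subset at below 1.5 versus 1.5 or above is optional and should be descriptive only, since the upper group may be small.

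Separately, the documents should state how the recommendation in Protocol 4.3 and exclusion 10 in Protocol 4.4 are meant to work together. This review does not propose a rule.

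The cost is SAP wording and one degree of freedom per model. No new data are needed.

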5.1.2 Visit 0 (Day -6, telephone contact): Pre-Baseline Daily Assessments

The following procedures will be performed:

- Review requirements for daily collection of WOMAC A pain evaluation using both the 5-point Likert scale and the 100mm VAS scale
- Confirm Baseline visit date
- It is possible, depending on the Baseline visit date and successful completion of Screening criteria defined above, that the first Pre-Baseline Daily Assessment may occur during the Screening visit.

5.1.3 Visit 1 (Day 0, in-clinic): Baseline/Randomization/Treatment

The following procedures will be performed:

- Confirm eligibility (review inclusion/exclusion criteria)
- Record concomitant medications
- Conduct pregnancy test, as applicable
- Perform and record physical examination
- Record vital signs (Measure body temperature, SBP, DBP, and pulse rate) pre- and post-injection
- Perform and/or review the final Pre-Baseline WOMAC A pain evaluation using both the 5-point Likert scale and the 100mm VAS scale
- Perform WOMAC B and C prior to treatment
- Perform PGA evaluations prior to treatment
- Randomize patient to study arm
- Perform intra-articular injection of blinded study treatment
- Record post-injection AEs if observed
- Issue rescue medication (acetaminophen [paracetamol])

5.1.4 Visit 2 (Day 1, telephone contact)

The following procedures will be performed:

- Record AEs
- Record concomitant medications
- Review rescue medication use

5.1.5 Visit 3 (Week 2 ± 7 days, telephone contact)

The following procedures will be performed:

- Perform WOMAC and PGA evaluations of the study knee
- Record AEs
- Record concomitant medications
- Review rescue medication use

5.1.6 Visit 4 (Week 4 ± 7 days, telephone contact)

The following procedures will be performed:

- Perform WOMAC and PGA evaluations of the study knee
- Record AEs
- Record concomitant medications
- Review rescue medication use

5.1.7 Visit 5 (Week 6 ± 7 days, in-clinic)

The following procedures will be performed:

- Perform and record physical examination
- Record vital signs. (Measure body temperature, SBP, DBP and pulse rate)
- Perform WOMAC and PGA evaluations of the study knee
- Record AEs
- Record concomitant medications
- Review rescue medication use

5.1.8 Visit 6 (Week 8 ± 7 days, telephone contact)

The following procedures will be performed:

- Perform WOMAC and PGA evaluations of the study knee
- Record AEs
- Record concomitant medications
- Review rescue medication use

5.1.9 Visit 7 (Week 10 ± 7 days, telephone contact)

The following procedures will be performed:

- Perform WOMAC and PGA evaluations of the study knee
- Record AEs
- Record concomitant medications
- Review rescue medication use

5.1.10 Visit 8 (Week 11 ± 7 days, telephone contact): Pre-Week 12 Daily Assessments

The following procedures will be performed:

- Review requirements for daily collection of WOMAC A pain scores using both the 5-point Likert scale and the 100mm VAS scale
- Confirm Week 12 visit date

5.1.11 Visit 9 (Week 12 ± 7 days, in-clinic)

The following procedures will be performed:

- Collect a urine sample for testing
- Perform and record physical examination
- Record vital signs. (Measure body temperature, SBP, DBP and pulse rate)
- Perform and/or review the final WOMAC A pain evaluation using both the 5-point Likert scale and the 100mm VAS scale
- Perform WOMAC B and C evaluations
- Perform PGA evaluations of the study knee
- Record AEs
- Record concomitant medications
- Review rescue medication use

5.1.12 Visit 10 (Week 24 ± 7 days, in-clinic)

The following procedures will be performed:

- Perform and record physical examination
- Record vital signs (Measure body temperature, SBP, DBP and pulse rate)
- Perform WOMAC and PGA evaluations of the study knee
- Record AEs
- Record concomitant medications
- Review rescue medication use

5.1.13 Early Termination Visit

The following procedures will be performed at Early Termination Visit:

- Perform and record physical examination
- Record vital signs. (Measure body temperature, SBP, DBP and pulse rate)
- Perform WOMAC and PGA evaluations of the study knee using both the 5-point Likert scale and the 100mm VAS scale
- Record AEs
- Record concomitant medications
- Review rescue medication use

5.1.14 Unscheduled Visits

Additional visits may be scheduled at the discretion of the Investigator, for example as part of follow-up of AEs. Unscheduled Visits will follow the visit structure described in Section 5.1.7 for the Week 6 visit.

5.1.15 Missed Visits

Patients unable to complete a study visit as scheduled should be re-scheduled for a replacement visit as soon as possible. If a subject misses any scheduled follow-up visit and cannot be seen within the +/- 7-day visit window, as described in [Table 6.1](#), the visit is considered missed.

6 METHODS OF ASSESSMENT

Demographic Data

At Visit 1(Screening), patient demographic data will be collected. These include year of birth, age, gender and race.

Medical History

At Visit 1(Screening) a complete medical history, including prior interventions to the study knee, will be obtained from each patient.

Concomitant Medications

Detailed history of medications will be documented for each patient at Screening and Baseline. Concomitant medications (especially any changes in medication) will be documented for each patient at each scheduled visit.

Physical Examination and Vital signs

Height in feet and inches will be measured at Screening.

Body weight in pounds (lb) will be measured at Screening.

Body temperature (deg F) will be measured at each visit.

SBP and DBP and pulse rate will be measured with the patient in a seated position.

The full physical examination will consist of examining the following body systems: cardiovascular, respiratory, abdominal, skin and musculoskeletal other than the knee. The physical examination of the target knee will consist of evaluating the knee joint for effusion and tenderness on palpation. [Table 6.1](#) below lists the various study activities and timing.

Biomarkers

At Week 12 urine samples will be collected and may be analyzed to compare differences between treatment groups for biomarkers, such as those for analgesic use and chemokines and cytokines associated with inflammation and cartilage regeneration.

